6.3.3 Technical device complaints

For device deficiencies or device malfunctions, the investigator will attempt to evaluate if the deficiency or malfunction might have led to an AE if suitable action had not been taken, intervention had not been made, or circumstances had been less fortunate. Complaints are defined as any written, electronic, or oral communication that alleges deficiencies related to the identity, quality, durability, reliability, safety, or performance of a medical device.

- A Device Technical Complaint form must be completed and submitted by the investigative site, irrespective of the seriousness of the case.
- A Device Technical Complaint form must be completed and submitted by the investigative site, irrespective of whether the complaint led to an AE.
- If a technical complaint is associated with an SAE, the investigative site must also

complete and submit an SAE form (see Section 6.2.4.2) in addition to the Device Technical Complaint form. SAE forms for device clinical trials should be sent to the sponsor for processing (as defined in Section 6.2.5).

Any technical complaints should be reported to the sponsor. The investigator will complete the Device Technical Complaint form and send it within 72 hours to Sinclair Vigilance team ([contact]) and Aesculape CRO for processing ([contact]).

If further sample analysis is requested, medical devices will need to be returned to the manufacturer:

Kylane Laboratories SA:

[name]

6.4 Safety Monitoring Plan

Subject's wellbeing and safety will be continuously taken into consideration during the trial period. If there is any contraindication observed during the interim of the study procedure that requires the discontinuation of the procedure, a decision should be made by the principal investigator (PI) and co- investigators to discontinue the subject from the study.

7 DATA ANALYSIS

7.1. Data Quality Assurance

7.1.1. Standardization procedures

Standardization procedures will be implemented to ensure accurate, consistent, complete, and reliable data, including methods to ensure standardization among sites (e.g., training, newsletters, investigator meetings, monitoring, centralized evaluations, and validation methods).

This study will be monitored regularly by a qualified monitor from the sponsor or its designee according to Good Clinical Practice (GCP) guidelines, ISO 14155:2020 and the respective Standard Operating Procedures (SOPs).

7.1.2. Data management

The investigator will prepare and maintain complete and accurate electronic Case Report Forms (eCRFs), recording all observations and data pertinent to the study for each subject. Data reported on eCRFs should be derived from source documents and must be consistent with the sources from which it derive. Investigators will sign and date the eCRFs as appropriate to verify the accuracy of the reported data. It is the responsibility of the investigator to ensure that all data are submitted to the sponsor in a timely manner.

7.1.3. Data review and clarification procedures

All data required by this clinical study protocol are to be entered into a validated database. Individual subject data are to be recorded in eCRFs within five days of each study visit.

By signing and dating the eCRFs, the investigator is confirming that all data entered were reviewed accurate and correct.

If corrections in the subject diary or questionnaires are necessary, the subject should be instructed to make a correction by drawing only a single line through the error, leaving the incorrect entry legible. The subject should date and initial the correction. The investigator should not make any changes to these documents

Essential documents should be retained per applicable regulations and as instructed by the study sponsor. Essential documents at the investigational site include, but are not limited to:

- Subject files
- Subject identification code list
- A copy of the study protocol and any amendments
- Investigator's copies of the eCRFs and any associated subject-related source data
- Signed Informed Consent Forms (ICFs)

- Copies of all direct correspondence with the Independent Ethics. Committee/Institutional Review Board (IEC/IRB) and with the regulatory authority(ies), and with the sponsor
- Copies of any photographs
- Copies of investigational device disposition records

Study documents may not be destroyed by study-site personnel prior to the end of the required retention period as specified by local regulations. The principal investigator (PI) or the institution must inform the sponsor in due time if the PI leaves the institution during the retention period. This rule also applies when the institution closes within the retention period.

7.1.4. Study auditing

To ensure compliance with applicable standards and regulations, the sponsor, or sponsor's designee, IEC/IRB, or regulatory authorities may conduct a quality assurance assessment or audit of site records at any time during or after completion of the study. In the event of an audit, investigators must grant access to all relevant documents (including source documents, electronic records, and other applicable study documentation) and always provide support for auditing activities.

7.2. Data Entry and Storage

All data shall be entered in English. The eCRFs should always reflect the latest observations on the subjects participating in the study. Therefore, the eCRFs shall be completed as soon as possible during (based on source documents) or after the subject's visit. The subject's identity must always remain confidential (i.e. the name and address of the subjects must not be registered in the eCRFs or in the study database). The investigator must verify that all data entries in the eCRFs are accurate and correct. If some assessments are not done, or if certain information is not available, not applicable, or unknown, the investigator will indicate this in the eCRF. The investigator shall electronically sign off on the study data. By signing, the investigator takes responsibility for the accuracy, completeness, and legibility of the data reported to the Sponsor in the eCRF.

8. SAMPLE SIZE AND STATISTICAL METHODS

8.1. Determination of Sample Size

The study population will include all subjects who are enrolled, and the entire study population will be included in statistical analysis.

Average Efficacy=85% Lower bound of 95% Confidence Interval (CI) =65% Clinical Margin=-20% Alpha=5% Power= 80% (Beta =0.20)

Considering 20% dropout rate, a total of 168 subjects (42 per site; a minimum of 36 per site respectively), to meet a completed study size requirement of 140, will be recruited.

- Mild to significant facial volume deficit (mid-face area) (n=60 (50), MaiLi Volume 30 (25) subjects and MaiLi Extreme 30 (25) subjects)
- Mild to moderate jawline ptosis (n=36 (30), MaiLi Extreme)
- Minimal to severe chin retrusion (n=36 (30), MaiLi Extreme)
- Minimal to severe temporal hollowing (n=36 (30), MaiLi Volume)

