This information serves as a support for the interest of further investigation of new HAs for use in midface, chin, jaw and temple.

MaiLi

The MaiLi product family is a line of four sterile, transparent, and resorbable cross-linked hyaluronic acid gels of bio-fermentation. The devices are intended to modify the anatomy and/or to alleviate a physiological process at the level of the face. Especially, the line has reconstructive purposes in treatment of facial changes associated with the aging process (i.e. mid-face volume deficit, jawline ptosis, chin retrusion, or temple hollowing) and other underlying conditions. The product family is represented by devices sharing the same mode of action and general intended use and based on the same established manufacturing technology.

The MaiLi range is indicated for intradermal, subcutaneous, and supraperiosteal application depending upon the product used and the indication targeted and submucosal implantation in the lips.

There are four products within the MaiLi family: Precise, Define, Volume and Extreme. All four products are HA fillers; cross-linked HA is suspended in a solution of phosphate buffer and lidocaine hydrochloride monohydrate with an overall concentration of HA ranging between 15 and 24mg/ml. The constituent HA is of bio-fermentation. All of the MaiLi products are formulated with sodium hyaluronate gel which has been cross-linked with 1,4-butanediol diglycidyl ether (BDDE).

The MaiLi range of products has demonstrated an excellent efficacy and safety profile in a clinical trial. All adverse device effects reported during the study were expected for injectable gels of hyaluronic acid and the vast majority of them lasted less than ten days. No Serious Adverse Event (SAE) occurred during the study. An independent evaluator and subjects reported significant improvements when treatment areas using the Global Aesthetic Improvement Scale (GAIS) were globally improved aesthetically one month, six months and twelve months after treatment: a twelve months post-treatment, with 81% of treated subjects showing improved, very improved, or exceptionally improved results in that period, with no top-up treatment performed ¹⁷.

MaiLi Volume

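### Section 8.1 states 80% power, but read per cohort the planned 25 or 30 completers give about 47–68% and 71% under the usual two-sided 95% intervals; only a Wald interval at 30 exceeds 80%

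*Protocol*

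**What the plan says.** Protocol section 8.1 gives its planning inputs in one line: "Average Efficacy=85% Lower bound of 95% Confidence Interval (CI) =65% Clinical Margin=-20% Alpha=5% Power= 80% (Beta =0.20". It then lists the cohorts, with completers in brackets: for mid-face, "MaiLi Volume 30 (25) subjects and MaiLi Extreme 30 (25) subjects"; for jawline, "Mild to moderate jawline ptosis (n=36 (30), MaiLi Extreme"; and the same 36 (30) for chin retrusion with MaiLi Extreme and for temporal hollowing with MaiLi Volume. Section 4.1 confirms that the bracketed figures are completers required per treatment group.

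The primary objective (sections 2.1 and 8.2) is the proportion improved on the GAIS at 6 months, set out by product and, within product, by indication.

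Section 8.1 names no formula, no interval method and no sidedness for alpha. It does not say whether the 80% belongs to each cohort, each product or the whole study.

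**The concern.** One power figure stands beside two cohort sizes, 25 and 30, although both share the same assumed rate, threshold and alpha. A proportion near 85% in so small a sample is also where a normal approximation to the binomial is least reliable. The question is whether a cohort of 25 or 30 would clear the 65% bound four times in five if the product performs as assumed.

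If it would not, the protocol credits the design with a sensitivity it lacks. A cohort whose lower limit falls below 65% could then be read against an advertised 80% power, when the miss was a likely result even at a true 85%.

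**Working it through.** **Inputs, all from section 8.1.** True rate 0.85 ("Average Efficacy=85"%); threshold 0.65 ("Lower bound of 95% Confidence Interval (CI) =65"%); difference 0.20 ("Clinical Margin=-20"%); alpha 5% and power 80%; 25 or 30 completers. A two-sided 95% interval puts 2.5% in the lower tail. The interval method is not given, so a range is shown.

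**Reproducing the plan's figure.** With the variance fixed at the assumed rate:

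n = (1.96 + 0.84)² × 0.85 × 0.15 / 0.20² = 7.849 × 0.1275 / 0.04 = 25.02 (7.849 uses unrounded normal quantiles)

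The same approximation gives 79.97% power at 25 and 86.6% at 30. So 25 is recovered, for a single cohort. The 30 is not recovered from this formula. The closest match found uses the null variance as well, with a one-sided 5% test (29.4). The same formula at two-sided 5% gives 38.2.

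**Power from the binomial.** For each method, take the smallest count whose two-sided 95% lower limit exceeds 0.65, then its upper-tail probability at p = 0.85. The error is the same tail at p = 0.65.

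| n | Method | Count needed (limit) | Limit one count lower | Power at 85% | One-sided error at 65% |
|---|---|---|---|---|---|
| 25 | Clopper-Pearson | 22 (0.688) | 0.639 | 47.1% | 1.0% |
| 25 | Wilson | 21 (0.653) | 0.609 | 68.2% | 3.2% |
| 25 | Jeffreys | 21 (0.663) | 0.616 | 68.2% | 3.2% |
| 25 | Wald | 21 (0.696) | 0.643 | 68.2% | 3.2% |
| 30 | Clopper-Pearson | 25 (0.653) | 0.614 | 71.1% | 2.3% |
| 30 | Wilson | 25 (0.664) | 0.627 | 71.1% | 2.3% |
| 30 | Jeffreys | 25 (0.673) | 0.633 | 71.1% | 2.3% |
| 30 | Wald | 24 (0.657) | 0.615 | 84.7% | 5.9% |

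At n = 25 the probabilities of 22, 23, 24 and 25 responders at p = 0.85 are 0.2174, 0.1607, 0.0759 and 0.0172, which sum to 0.471. Adding 0.2110 for 21 responders gives 0.682.

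**Why the formula overstates power at 25.** It fixes the standard error at √(0.1275/25) = 0.0714, so 20/25 would pass: 0.80 − 1.96 × 0.0714 = 0.660. An actual Wald interval uses the observed proportion, with standard error √(0.80 × 0.20/25) = 0.080, so 20/25 fails: 0.80 − 1.96 × 0.080 = 0.643. The count needed moves to 21 and power falls to 68.2%.

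**All enrolled subjects analysed.** With Clopper-Pearson, 30 enrolled needs 25 responders (71.1%) and 36 enrolled needs 30 (71.0%).

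**Size at which 80% is met.** With Clopper-Pearson, 80% is first reached at n = 41 (33/41, 84.8%) and holds at every n from 45.

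**The case against.** **The plan's number can be reproduced, so it is not an arithmetic slip.** This stands: 25 follows from a standard approximation. But the figure claimed is the probability of clearing a 95% lower bound, and even the Wald interval that belongs with that formula gives 68% at n = 25. Naming an interval later in an SAP would not rescue it, since none of the methods tried reaches 80% at 25.

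**The 80% may not be per cohort.** The text does not say, and the objective is bulleted by product. With Clopper-Pearson, power would be 88.7% for Volume (25 + 30 = 55 completers) and 98.7% for Extreme (25 + 30 + 30 = 85). The unit therefore remains an inference. The match at 25.02 and the naming of each indication favour the cohort; no product total is recovered from the inputs at 80%.

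**Alpha may be one-sided 5%.** Section 8.1 refers to a 95% interval, without stating sidedness. Even at one-sided 5%, Clopper-Pearson gives 68.2% at 25 and 71.1% at 30. Wald reaches 83.9% at 25 with an actual error of 8.3%. Wilson, Jeffreys and Wald reach 84.7% at 30 with an actual error of 5.9%.

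**The analysed number may be larger.** Section 8.1 includes everyone enrolled, completers are counted over 24 months while the endpoint is at 6, and subjects may be treated in more than one area. This is fair. At 36, Wald and Jeffreys give 84%, although Clopper-Pearson and Wilson stay at 71%. Extra subjects from multi-area treatment are not planned for or counted, so they cannot support the stated power.

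**47% is a severe case.** It is specific to the more conservative methods, and 25 is a low point of a jagged curve: Clopper-Pearson gives 65% at n = 26. The 47% should never be quoted without its method.

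**Conclusion.** Read per cohort, the stated 80% power is not delivered. At 25 completers it is 47% (Clopper-Pearson) to 68% (Wilson, Jeffreys, Wald), below 80% for every two-sided 95% method tried. At 30 it is 71% for Clopper-Pearson, Wilson and Jeffreys. Wald alone exceeds 80%, by letting the one-sided error rise to 5.9% against 2.5%. The conclusion assumes a true rate of 85%, a two-sided 95% interval and power meant for each product-indication cohort; the first is stated, the second is the natural reading and the third is inferred.

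Three stronger readings are not supported. A reader might take 47% and 71% as true of any 95% interval; they are not. A reader might ask how often all five cohorts would succeed together; the protocol sets no such requirement, and cohorts that share multi-area subjects need not be independent. A reader might repeat the calculation at the background section's result, "with 81% of treated subjects showing improved, very improved, or exceptionally improved results in that period"; that is a 12-month figure for the MaiLi range, and section 3 shows that the pilot included other products and areas, so it does not set a 6-month rate for Volume or Extreme here.

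**What to change.** Keep the enrolment. In section 8.1, name the interval method, state that the power applies to each product-indication cohort, and replace the single 80% with the actual figures. For example: *with an exact (Clopper-Pearson) two-sided 95% CI, power to exclude 65% at a true rate of 85% is 47% in cohorts of 25 completers and 71% in cohorts of 30*. If another interval is chosen, give its power and its actual error at these sizes.

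If the sponsor wants a 65% criterion with at least 80% power at the present size, a product-level proportion (55 Volume and 85 Extreme completers) is an option. It changes what is tested, and it would need a rule for combining the ratings of a subject treated in more than one area.

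The cost of the main change is a rewording of section 8.1 and less favourable power figures, with no extra subjects.

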Trial Design	The study is a 24-month, open-label, prospective, post-market clinical follow- up trial (PMCF), with two treatment groups. One group will receive the MaiLi Extreme. The study will be conducted in 4 European study sites, located in Belgium and Germany. The study consists of 5 visits to assess efficacy at month 3, month 6, month 12, month 18, and month 24. And consists of 6 visits to assess safety at week 2, month 3, month 6, month 12, month 18, and month 24. The trial requires 140 subjects that complete the study visits. Taking into account a drop-out rate of 20%, 168 subjects will have to be recruited (42 per site; a minimum of 36 per site respectively). Eligible subjects include female or male subjects between the ages of 25 and 65 years of age inclusively across a range of Fitzpatrick skin types. In the MaiLi Volume treatment arm, 30 subjects will be assigned for treatment of mid-face volume deficit and 36 subjects of temple hollowing. In the MaiLi Extreme treatment arm, 30 subjects will be assigned of treatment of mid-face volume deficit, 36 subjects of jawline ptosis, and 36 subjects of chin retrusion. However if subjects meet the inclusion criteria, they have the option to receive injections in multiple treatment areas and generate data for more than one treatment indication.
Sample Size	168 subjects recruited (42 per site; a minimum of 36 per site respectively), over 4 investigational study sites, to meet a sample size of 140 subjects completing the study.
Summary of Eligibility Criteria	Subjects who meet all inclusion- and no exclusion criteria are eligible for participation in the clinical study.
	Eligible subjects include males and females aged 25-65 years inclusively across a range of Fitzpatrick skin types, defined as (the completed study size requirements for each treatment group are provide in brackets):

 mild to significant facial volume deficit (mid-face area) (n=60 (50), MaiLi Volume 30 (25) subjects and MaiLi Extreme 30 (25) subjects)

or

 mild to moderate jawline ptosis (n=36 (30), MaiLi Extreme)

or

• minimal to severe chin retrusion (n=36 (30), MaiLi Extreme)

or

 minimal to severe temporal hollowing (n=36 (30), MaiLi Volume)

Subjects can be treated in multiple areas if they meet the required inclusion criteria, but cannot be treated with both MaiLi Volume and Extreme.

Inclusion Criteria

Subjects meeting all of the following criteria are eligible for participation in this clinical study:

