4. STUDY POPULATION

4.1. List the number and nature of subjects to be enrolled.

A total of 168 subjects (42 per site; a minimum of 36 per site respectively), to meet a completed study size requirement of 140, will be recruited across four sites in Europe. The completed study size requirements for each treatment group are provided in brackets. Male or female subjects between the ages of 25 and 65 years of age inclusively across a range of Fitzpatrick skin types having:

• mild to significant facial volume deficit (mid-face area) (n=60 (50), MaiLi Volume 30 (25) subjects and MaiLi Extreme 30 (25) subjects)

or

• mild to moderate jawline ptosis (n=36 (30), MaiLi Extreme)

or

• minimal to severe chin retrusion (n=36 (30), MaiLi Extreme)

or

• minimal to severe temporal hollowing (n=36 (30), MaiLi Volume)

Subjects can be treated in multiple areas if they meet the required inclusion criteria, but cannot be treated with both MaiLi Volume and Extreme. The lead area the subject will be treated, need to be decided by the investigator for recruitment purposes. For example, if a subject meets the inclusion criteria for treatment for temple hollowing and would like to receive treatment in this area in addition to the mid-face, then the use of MaiLi Volume would allow treatment in both areas. If the lead treatment area is judged by the investigator to be volumization of the mid-face, then for the purposes of recruitment, the subject will be assigned to the mid-face group, even though they are treated in both areas.

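### The 20% drop-out allowance is applied as n × 1.20 instead of n/(1 − 0.20), so 168 recruits are expected to give about 134 completers, not the required 140

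*Protocol*

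**What the plan says.** The synopsis (Trial Design) fixes the target: "The trial requires 140 subjects that complete the study visits". It then gives the recruitment: "Taking into account a drop-out rate of 20%, 168 subjects will have to be recruited". Section 8.1 repeats both figures and the rate: "Considering 20% dropout rate, a total of 168 subjects", "to meet a completed study size requirement of 140, will be recruited". Section 4.1 gives the same 168 for 140 without restating the rate, and explains the cohort notation: "The completed study size requirements for each treatment group are provided in brackets".

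On that notation, section 8.1 lists the mid-face cohorts as "n=60 (50), MaiLi Volume 30 (25) subjects and MaiLi Extreme 30 (25) subjects" and the jawline cohort as "Mild to moderate jawline ptosis (n=36 (30), MaiLi Extreme". The chin and temple cohorts carry the same 36 (30). The five cohorts add up to the totals: 30 + 30 + 36 + 36 + 36 = 168 recruited and 25 + 25 + 30 + 30 + 30 = 140 completed.

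**The concern.** A 20% drop-out rate means that one in five of the subjects recruited does not finish. To end with n completers, one must therefore recruit n/(1 − 0.20). Adding 20% of the completers to the completers gives a smaller number. All the protocol's recruited figures look as if they were obtained in that second way.

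If so, the plan contradicts itself. The completed size is presented as a requirement, and the stated recruitment is not expected to deliver it under the stated drop-out. Anyone who later judges retention against the 20% allowance would believe that the study is on target when it is already below it.

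**Working it through.** **Inputs, all from the protocol.** Drop-out 20% (synopsis, section 8.1). Recruited (completed): total 168 (140); mid-face Volume 30 (25); mid-face Extreme 30 (25); jawline, chin and temple 36 (30) each (synopsis, sections 4.1 and 8.1).

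**Step 1. Reproduce the plan's figures.** With recruited = completed × (1 + 0.20):

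- 140 × 1.20 = 168
- 25 × 1.20 = 30
- 30 × 1.20 = 36

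All figures are matched exactly, so this is one consistent method and not rounding.

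**Step 2. Expected completers at 20% drop-out.** With completers = recruited × (1 − 0.20):

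| Group | Recruited | Expected completers | Stated requirement | Shortfall |
|---|---|---|---|---|
| Total | 168 | 134.4 | 140 | 5.6 |
| Each mid-face cohort | 30 | 24.0 | 25 | 1.0 |
| Jawline, chin, temple, each | 36 | 28.8 | 30 | 1.2 |

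**Step 3. Drop-out that the stated recruitment allows for.** 1 − 140/168 = 1 − 25/30 = 1 − 30/36 = 16.7%.

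**Step 4. Recruitment that 20% would need.** 140/0.80 = 175. By cohort, 25/0.80 = 31.25, so 32; and 30/0.80 = 37.5, so 38. With whole subjects per cohort the total is 2 × 32 + 3 × 38 = 178.

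**Step 5. Chance of reaching the requirement.** Assume that subjects drop out independently at a common rate d. The number of completers is then binomial with probability 1 − d.

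| d | P(at least 140 of 168) | P(at least 25 of 30) | P(at least 30 of 36) |
|---|---|---|---|
| 10% | 0.997 | 0.927 | 0.937 |
| 16.7% | 0.550 | 0.616 | 0.607 |
| 20% | 0.163 | 0.428 | 0.401 |

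The 20% row is the plan's own assumption. The other rows show how strongly the result depends on the true rate.

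**Step 6. Whether power moves.** Section 8.1 names no test, so this step rests on assumed ones, taking 85% against 65%.

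- A Wald calculation with two-sided 5% uses power = Φ(0.20/√(0.85 × 0.15/n) − 1.96). It gives 80.0% at 25 and 78.3% at 24, and 86.6% at 30 and 85.2% at 28.8.
- An exact binomial test at one-sided 2.5% gives 47.1% at 25 and 50.5% at 24. It gives 71.1% at 30, 55.5% at 29 and 58.7% at 28. Exact power is not monotone in n, because the attainable significance level jumps from one n to the next.

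**The case against.** The strongest case is that little follows from the slip, and several parts of that case stand.

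- **Time point.** The 140 are subjects who complete the study visits, which run to month 24, while the primary efficacy endpoint is GAIS at month 6. If loss by month 6 is at most 16.7%, the expected month-6 numbers meet every bracketed figure. This stands as a limit on the consequence. It does not rescue the sum, because the protocol gives no month-6 drop-out rate and ties the 20% to completing the study.
- **Analysis population.** Section 8.1 says that everyone enrolled will be analysed, so completers may not be the only source of information. That is fair, but it does not turn 168 recruits into 140 completers at 20% loss.
- **Several treated areas.** Subjects may contribute data to more than one indication, so the numbers analysed per indication can exceed the lead-area counts. The cohort shortfalls therefore apply to lead-area counts, which section 4.1 uses for recruitment. The total of 140 is a count of subjects and gains nothing from this.
- **Planning allowance.** The 20% may be cautious, and at 10% the target would almost certainly be met. It is still the rate that the plan states.

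Two stronger readings are tempting. A reader might infer that every cohort will miss its size. The documents support only an expected shortfall: at exactly 20%, a single cohort still reaches its target with a probability of 40% to 43%. A reader might also infer that the slip lowers cohort power throughout. That is not shown. No test is named, the Wald loss is under two percentage points, and under the exact test a mid-face cohort of 24 has slightly more power than one of 25.

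**Conclusion.** The sample-size statement is wrong as written. The recruited figures correspond to 16.7% drop-out and not to 20%. Nothing in the protocol redefines drop-out as a fraction of completers. Under the stated 20%, the expected shortfall is 5.6 completers of 140 (4%) and 1.0 to 1.2 per cohort by lead area. Reaching 140 has a probability of about 16%, if drop-outs are independent at exactly that rate.

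The shortfall is small and concerns completion of the 24-month study. What it does to the month-6 primary endpoint cannot be determined, because the timing of drop-out is not given. The finding is an arithmetic inconsistency that should be corrected. It does not show that the design fails.

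**What to change.** Make the same correction in the synopsis, section 4.1 and section 8.1, in one of two ways:

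1. Keep 168 recruited and 140 completed (30 for 25, 36 for 30 by cohort), and state that this allows for 16.7% drop-out.
2. Keep the 20% rate and 168 recruited, and restate the expected completers as about 134: 24 in each mid-face cohort and 28 to 29 in each of the jawline, chin and temple cohorts. Then check that the stated 80% power still holds at those numbers under the intended test.

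The cost is a text change in three places, plus a short power check under the second option. The stated allowance or the expected yield becomes slightly less favourable. No extra enrolment is needed.
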